1. SYNOPSIS

Study Title	'Simulation-based Arthroscopic Surgery Programme' (MSD-IDREC-C1-2014-152)	
Internal ref. no. / short title		
Study Design	Educational observational study	
Study Participants	Healthy Volunteers from junior surgical trainees, and their consultants, working within the Oxford Deanery (Health Education Thames Valley)	
Planned Sample Size	60 per year	
Planned Study Period	5 years (to 2019)	
	Objectives	Outcome Measures
Primary	Assess the usefulness to training of the new elbow-attached motion sensors during diagnostic knee arthroscopy as part of routine consultant-supervised training in theatre	Motion data, Global Rating Scales, Surgical logbook data
Secondary	Assess the usefulness to training of the new elbow-attached motion sensors during simulated arthroscopy in the skills lab	Motion data, Surgical logbook data

2. ABBREVIATIONS

CCT	Certificate of Completion of Training
CI	Chief Investigator
CRF	Case Report Form
CTRG	Clinical Trials & Research Governance, University of Oxford
GCP	Good Clinical Practice
GMC	General Medical Council
GP	General Practitioner
GRS	Global Rating Scale
HETV	Health Education Thames Valley
ICF	Informed Consent Form
MAT	McLaren Applied Technology
NHS	National Health Service
NRES	National Research Ethics Service

OOSEC	Oxford Orthopaedic Simulation and Education Centre
PI	Principal Investigator
PIL	Participant Information Leaflet
R&D	NHS Trust R&D Department
REC	Research Ethics Committee
SAC	Specialty Advisory Committee
SOP	Standard Operating Procedure

3. BACKGROUND AND RATIONALE

The 'Simulation-based Arthroscopic Surgery Programme' MSD-IDREC-C1-2014-152 aims to gather evidence for simulation training during surgical training. On a background of decreasing working time available, less independent operating, and greater public expectations of the medical profession, simulation is seen as an important support to routine surgical training. However, there is little evidence to show it improves surgical performance, and studies not been based on truly objective measurements. The 'Simulation-based Arthroscopic Surgery Programme' has the primary aim of developing evidence-based simulation training by objectively justifying the use of simulation to improve surgical training.

At the Oxford Orthopaedic Simulation and Education Centre (OOSEC) we are investigating new training methods for our future surgeons and using simulators, cadaver specimens and virtual reality models. To ensure evidenced based training we assess the learning and performance of the trainee groups using these various simulators. These groups mainly compromise surgical trainees, consultants and medical students and NHS ethics is not required, however to ensure best practice and as this work can lead to educational publications, we have ethical approval in place from CUREC (Simulation-based Arthroscopic Surgery Programme; MSD-IDREC-2014-152). In addition, and as part of an educational project, we will assess trainees in the real operating theatre as part of their usual training with their consultants, while patients receive their normal treatment.

Motion analysis is a validated objective measure of technical skill used previously in simulated settings: numbers of hand movements and total path length have been shown to decrease with surgeon experience during simulated tasks. Typically, motion analysis involves wired sensors attached to the wrists that are unsuitable for use in theatre as the position interferes with sterile scrubbing. Our group has developed simple elbow-worn wireless motion sensors: besides using these sensors in the simulated setting it is now possible to also use them in the real operating theatre while trainees under go their normal training and assessments.

Our study has CUREC approval to use surgical trainees as volunteers, and for technical skills assessments to take place in a simulated setting: we are seeking additional Trust approval to use elbow-worn wireless motion sensors during a routine consultant-supervised training list in the real operating theatre as an objective form of educational monitoring in addition to the methods already in use in their training programme curriculum portfolios (e.g. Practice-based Assessments, Directly Observed Procedures, Global Rating Scales). For the purpose of completeness, we also detail the specific features of this study

as part of the Simulation-based Arthroscopy Programme which occur in the simulated setting in the study description below.

The sensors only gather surgical movement data and the trainers and trainees can then review their performance after the case to better understand and improve their training. The sensors themselves are safe to use in a clinical environment. They are securely attached to the surgeon's elbows and do not interfere with thorough surgical scrubbing, nor do they interfere with any theatre equipment. They do not make contact with the patient, and are not attached or implanted in the patient. They do not involve the collection of any patient identifiable data, nor storage of tissue samples. As such, they pose no risk or interruption to standard theatre procedure.

This study aims to investigate the use of a new form of educational monitoring during normal clinical practise, and this does not interfere with the delivery of normal patient care nor usual surgical practise.

Risks: The presence of these sensors in theatre poses no additional risks or interruption to standard theatre procedure.

Benefits: Participants will gain an understanding of their technical dexterity and skill. This may indicate areas of focus for practice, and may benefit patients by improving the learning curve in surgical trainees. They will make further possible the development of national evidenced based guidelines for arthroscopy training.

Population: The participants wearing these sensors will be a mixture of core surgical trainees and specialist registrars on approved surgical training programmes, and their consultant supervisors. Typically these will be young healthy adults.

Generalisable findings: Initially we aim to assess the motion parameters associated with diagnostic knee arthroscopy (a single repeatable arthroscopic tasks), but the concept and techniques of in theatre motion analysis could be generalised to all procedures where technical skills are required. The use of motion analysis intra-operatively means that surgical competence could be defined in terms of motion analysis parameters. Correlation between simulated and intra-operative measurements of these motion analysis parameters could be used to define a proficiency criterion in simulated pre-patient training before performing surgery in theatre, or motion analysis parameter correlation with the number of procedures performed could be used to advise the SAC when defining the indicative numbers of procedures required to achieve CCT.

4. OBJECTIVES AND OUTCOME MEASURES

Objectives	Outcome Measures	Timepoint(s) of evaluation of this outcome measure (if applicable)

Primary Objective Assess the usefulness of the new elbow-attached motion sensors during diagnostic knee arthroscopy as part of routine, consultant-
	
Motion analysis parameters during consultant-supervised diagnostic knee arthroscopy
 
Global rating scale during consultant-supervised diagnostic
	
At 3 months follow up, as part of and during the CUREC-approved 'Simulation-based Arthroscopic Surgery Programme' MSD-IDREC-2014-152

supervised training in theatre	knee arthroscopy	
Secondary Objective Assess the usefulness to training of the new elbow-attached motion sensors during simulated arthroscopy in the skills lab	Motion analysis parameters during simulated arthroscopy in the Skills lab	At baseline and after 3 months,

5. STUDY DESIGN

The ‘Simulation-based Arthroscopic Surgery Programme’ MSD-IDREC-2014-152 is a CUREC-approved series of studies investigating the effect of new training methods for our future surgeons and using simulators, cadaver specimens and virtual reality models. These studies involve the assessment of trainee groups (including junior surgical trainees, specialist registrars and consultants) in two ways:

- 1 – on simulators, using metrics such as motion analysis data, global rating scales and participant feedback
- 2 – in theatre, using metrics such as global rating scales, procedure based assessments and participant feedback.

In this particular sub-study, we are recruiting up to 60 junior surgical trainees in T&O posts as part of their training programme. These will all undergo a baseline assessment on an arthroscopic simulator, after which they will be randomised 50:50 to either a control group (regular training i.e. their T&O post) or an experimental group (additional simulation training approx.. 1 hour per week) for the next three months. At 3 months they will undergo repeat assessment on the arthroscopic simulator, and in theatre.

Participants will use simple elbow-worn wireless motion sensors during simulation assessments and simulation training, and during usual training in theatre under consultant-supervision, while the patients received their normal treatment, to assess their effectiveness at monitoring learning and performance in addition to the usual forms of educational monitoring above. Over the course of the study, surgical logbook/training data will be collected by the participant and linked to their other results anonymously.

6. PARTICIPANT IDENTIFICATION

6.1. Study Participants

Healthy volunteers from the deanery training programme at junior surgical trainee and specialist registrar level, plus consultant orthopaedic surgeons

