6.2. Inclusion Criteria

- Participant is willing and able to give informed consent for participation in the study.
- Healthy adults, Male or Female, aged 18 years or above.
- Enrolled in Health Education Thames Valley/Oxford Deanery Training Programme in junior surgical training posts; or supervising Orthopaedic Consultant.

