7.2. Screening and Eligibility Assessment

The invitation emails will be sent to those who fit the recruitment group by the Deanery and the Trust. Of those responding and expressing an interest, the eligibility criteria (namely employed in a T&O post at a junior surgical level in the OUH Foundation Trust; consenting to take part) will be confirmed before proceeding to arrange any assessments.

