7.4. Randomisation

At the first meeting after their baseline simulation assessment, they will be randomised by sealed envelopes method to either control or experimental groups. As the participant will be attending simulation training, they cannot be blinded to this, but they will be provided with a unique identifier for use during the motion capture which will allow the data to be recorded anonymously and analysed blindly as to the randomisation.

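### The participant descriptions conflict over specialist registrars, and surgical experience, which the protocol says drives the motion metrics, is used neither in allocation nor in the planned between-arm theatre test

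*Combined protocol and SAP*

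**What the plan says.** **Who takes part.** Section 6.1 gives the participants as "Healthy volunteers from the deanery training programme at junior surgical trainee and specialist registrar level, plus consultant orthopaedic surgeons". The population paragraph of Section 3 says "The participants wearing these sensors will be a mixture of core surgical trainees and specialist registrars on approved surgical training programmes, and their consultant supervisors". The withdrawal list in Section 7.7 also refers to higher as well as core training.

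Other sections are narrower. The synopsis lists junior surgical trainees and their consultants. Section 5 says "In this particular sub-study, we are recruiting up to 60 junior surgical trainees in T&O posts as part of their training programme" and randomises that group; Section 7.1 repeats the cohort. Section 6.2 admits those "in junior surgical training posts; or supervising Orthopaedic Consultant", and Section 7.2 gives the screening rule as "namely employed in a T&O post at a junior surgical level in the OUH Foundation Trust; consenting to take part". Sections 5 and 7.1 name registrars as a separate group, and only for the wider programme. No section says which grades count as junior.

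**How experience is handled.** Section 3 states that hand movements and path length decrease as surgeons gain experience. Section 7.3 collects simulator motion data and information on surgical experience at the baseline session. Section 7.4 then says that "they will be randomised by sealed envelopes method to either control or experimental groups"; it mentions no stratification or blocking. Section 4 places the theatre outcomes at 3 months only, whereas the simulator outcome also has a baseline. Section 8.1 compares groups by Mann-Whitney U or Kruskal-Wallis tests and reports motion performance with reference to experience, without an adjusted analysis.

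**The concern.** There are two linked problems.

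First, a reader cannot tell from Section 6.1 what part a registrar plays. Section 7.6 describes only two roles in theatre: the participant who is assessed and the consultant who supplies the benchmark. A registrar admitted under 6.1 therefore has no stated role outside the randomised pathway, while 6.2 and 7.2 do not admit one.

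Second, the protocol names experience as a determinant of its own outcome and records it before the envelope is opened, then makes no use of it in allocation or in the planned test. In theatre there is no earlier measurement to correct for a difference in starting level. The consultant benchmark in Section 7.6 is meant for differences between cases, such as the size of the leg, and not for differences between trainees. If the arms happen to differ in experience, the planned test cannot separate that difference from an effect of simulation training. This second problem does not depend on registrars, because Section 6.2 sets no limit on earlier arthroscopies and juniors can differ in experience too.

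**Working it through.** The plan gives no alpha, power, effect size or SD, so there is no stated figure to reproduce. Sixty is a recruitment ceiling.

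**Inputs from the documents:** up to 60 randomised 50:50 (Section 5), so 30 per arm at most; no stratification stated (7.4); unadjusted rank tests (8.1); theatre outcome at 3 months only (4).

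**Assumptions:** K experienced trainees among those randomised; an experience effect of 0.5 to 1.5 within-group SD on a motion metric; a two-sided 5% test. None of these is in the documents.

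**1. Chance of imbalance.** With N = 60 and 30 per arm, the number X of experienced trainees in one arm is hypergeometric (60, K, 30), and the arms differ by |2X − K|. A difference of 6 is 6/30 = 20 percentage points.

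| N | K | Difference | Probability |
|---|---|---|---|
| 60 | 10 | 6 or more | 8.0% |
| 60 | 12 | 6 or more | 10.4% |
| 60 | 20 | 4 or more (13 points) | 41.2% |
| 60 | 20 | 6 or more (20 points) | 17.0% |
| 60 | 30 | 6 or more | 19.6% |
| 30 | 10 | 20 points or more | 24.5% |

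These are two-sided. For K = 20, an imbalance of 6 or more towards one given arm has probability 17.0%/2 = 8.5%.

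**2. Size of the shift.** Shift = difference in share × experience effect.
- 6 trainees: 6/30 × 1.0 to 1.5 SD = 0.20 to 0.30 SD.
- 4 trainees: 4/30 × 1.0 to 1.5 SD = 0.13 to 0.20 SD.

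For scale, the standard error of the arm difference at 30 per arm is √(2/30) = 0.26 SD.

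**3. Error rate of the planned test.** Simulation with 20,000 replicates per setting: normal outcome, no training effect, 30 per arm, K = 20 or 30, Mann-Whitney U. Overall type I error with unstratified allocation was 4.8% to 5.1% throughout.

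| Experience effect | Type I error given imbalance of 20 points or more | Type I error, stratified allocation with unadjusted test |
|---|---|---|
| 0.5 SD | 6.4–6.6% | 4.3% |
| 1.0 SD | 9.9–10.1% | 2.7–3.0% |
| 1.5 SD | 14.8–15.2% | 1.4–1.8% |

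Given a smaller imbalance, the rate under unstratified allocation was 2.6% to 4.7%. The last column shows that stratifying the envelopes while keeping the unadjusted test makes that test conservative.

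**4. Precision.** With experienced share p and effect d, outcome variance rises from 1 to 1 + p(1 − p)d² if experience is ignored. Removing that term cuts the SD of the arm difference by 1 − 1/√(1 + p(1 − p)d²).
- p = 1/3: d = 1.0 gives 1 − 1/√1.222 = 10%; d = 1.5 gives 1 − 1/√1.5 = 18%.
- p = 1/2: d = 1.0 gives 1 − 1/√1.25 = 11%; d = 1.5 gives 1 − 1/√1.5625 = 20%.

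**The case against.** A reader might infer that registrars are randomised from the same envelopes as first-year trainees. The documents do not support that. Section 5 recruits and randomises junior trainees, Section 7.1 repeats this, and Sections 6.2 and 7.2 restrict the trainees to junior posts. Sections 3 and 6.1 say who wears sensors or takes part, not who is allocated. The amendment history records a change of population to junior orthopaedic trainees, so the registrar wording may simply be left over. This stands: the conflict is over who is a participant, and the repair is editorial. The undefined word "junior" still leaves the boundary open.

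A reader might also infer that unstratified envelopes bias the comparison. They do not. Chance imbalance is already part of the test's error rate, which stays near 5% overall, and half of all imbalances would hide a training effect rather than mimic one. The illustrative shift of 0.2 to 0.3 SD is about one standard error. The assumed spread of experience is also less plausible if only juniors are randomised.

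Experience, baseline simulator data and logbook data are all collected and linked, so an imbalance would be visible and adjustment would be possible. But Section 8.1 commits only to reporting against experience.

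Finally, the primary objective is the usefulness of the sensors, and no contrast between arms is named as primary. That lowers the stakes. The plan nevertheless randomises and provides for between-group tests, so the comparison should be sound.

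**Conclusion.** The concern holds in a limited form. The participant descriptions in Sections 3 and 6.1 do not agree with the synopsis or Sections 5, 6.2, 7.1 and 7.2, and must be reconciled. Separately, a recorded factor that the protocol itself says drives the outcome is left out of both the allocation and the planned theatre test.

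The cost is lost precision (an SD of the arm difference that could be about 10% to 20% smaller for experience effects of 1.0 to 1.5 SD) and a conditional risk. If an imbalance of 20 points or more occurs, the false-positive rate is about 6% to 15% for effects of 0.5 to 1.5 SD. Such an imbalance arises in 17% of allocations if 20 of 60 are experienced, and in 8% or 20% if 10 or 30 are. These sizes rest on an assumed experienced share and SD gap. The qualitative point rests only on the protocol's own statement that the metrics change with experience.

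**What to change.** 1. **Sections 3, 6.1 and 7.7:** bring these into line with Sections 5, 6.2 and 7.2. State that only junior trainees are randomised, define that term by grade, and say that any registrars or consultants take part as non-randomised comparison or benchmark participants.
2. **Section 7.4:** prepare envelopes in two strata of prior knee arthroscopy experience, as recorded at the baseline session, each in permuted blocks. Choose the cut-point so that both strata are populated; a split of none against any may leave one nearly empty among juniors.
3. **Section 8.1:** replace the unadjusted between-arm theatre test with one stratified by the same factor, such as the van Elteren test, or with a rank or regression analysis adjusted for experience and baseline simulator score. Without this step, stratified envelopes make the planned test conservative.

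The cost is wording in these sections, a second set of envelopes, one experience question that must be answered before the envelope is opened, and slightly more analysis work. Section 7.3 already provides for collecting the data.

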6.2. Inclusion Criteria

- Participant is willing and able to give informed consent for participation in the study.
- Healthy adults, Male or Female, aged 18 years or above.
- Enrolled in Health Education Thames Valley/Oxford Deanery Training Programme in junior surgical training posts; or supervising Orthopaedic Consultant.

6.3. Exclusion Criteria

The participant may not enter the study if ANY of the following apply:

- Unwilling or unable to provide informed consent

7. STUDY PROCEDURES

7.1. Recruitment

The 'Simulation-based Arthroscopic Surgery Programme' MSD-IDREC-2014-152 recruits junior surgical trainees, specialist registrars, and their supervising consultants from the Oxford Deanery for simulation training using simple elbow-worn wireless motion sensors. Recruitment takes place using emailed adverts sent via clinical and academic departments e.g. newsletters. In this particular sub-study, we are recruiting up to 60 junior surgical trainees in T&O posts as part of their training programme. Those who express an interest to the invite circulated by the Deanery/Trust will be provided with a participant information sheet and have the opportunity to discuss this with an investigator. Those wishing to proceed will be invited to attend a baseline session where eligibility and consent are confirmed in person after the participant has the opportunity to ask any further questions regarding the study or participant information sheet.

7.2. Screening and Eligibility Assessment

The invitation emails will be sent to those who fit the recruitment group by the Deanery and the Trust. Of those responding and expressing an interest, the eligibility criteria (namely employed in a T&O post at a junior surgical level in the OUH Foundation Trust; consenting to take part) will be confirmed before proceeding to arrange any assessments.

7.3. Baseline assessment

The first session will be a baseline meeting where eligibility and consent are confirmed once the participants questions regarding the previously provided information sheet are answered. Baseline simulator performance data using motion analysis will be gathered, plus some basis demographic data and information about surgical experience. They will also be asked to keep a note of all surgical procedures they perform in the coming 3 months. They will also be randomised to the control (usual training) or experimental (additional simulation training) group. This meeting will take about 45-60 minutes.

7.4. Randomisation

At the first meeting after their baseline simulation assessment, they will be randomised by sealed envelopes method to either control or experimental groups. As the participant will be attending simulation training, they cannot be blinded to this, but they will be provided with a unique identifier for use during the motion capture which will allow the data to be recorded anonymously and analysed blindly as to the randomisation.

7.5. Informed Consent

For each study in the 'Simulation-based Arthroscopic Training Programme' the participant must personally sign and date the latest approved version of the Informed Consent form before any study specific procedures are performed. This takes place at the baseline assessment.

Written and verbal versions of the Participant Information and Informed Consent will be presented to the participants detailing no less than: the exact nature of the study; the presence of randomisation in the protocol; what it will involve for the participant; the implications and constraints of the protocol; the known side effects and any risks involved in taking part. It will be clearly stated that the participant is free to withdraw from the study at any time for any reason without prejudice to future care, without affecting their legal rights, and with no obligation to give the reason for withdrawal.

The participant will be allowed as much time as wished to consider the information, and the opportunity to question the Investigator, or other independent parties to decide whether they will participate in the study. Written Informed Consent will then be obtained by means of participant dated signature and dated signature of the person who presented and obtained the Informed Consent. The person who obtained the consent must be suitably qualified and experienced, and have been authorised to do so by the Chief/Principal Investigator. A copy of the signed Informed Consent will be given to the participant. The original signed form will be retained at the study site.

